# 9.2 Endpoints of study analysis

# 9.2.1 Primary endpoints

# 9.2.1.1 Efficacy

- Progression-free survival (PFS) based on independent radiologic review: assess PFS according to "RECIST v1.1-GIST Specific Standard" which include:
  - Lymph nodes cannot be taken as target lesions; enlarged lymph nodes will be followed as non-target lesions.
  - Bone lesions cannot be taken as target lesions;
  - Positron emission tomography (PET) cannot be used in efficacy assessment;
  - According to "RECIST v1.1-GIST Specific Standard", new tumor nodules within the pre-existing tumor lesion that are gradually growing must meet the following criteria before being determined as definite progression: (a) The lesion diameter should be at least 2 cm and confirmed as active GIST lesion (for example, using contrast or other criteria for enhanced scanning to rule out the possibility of false appearance); Or (b) At least 2 consecutive radiographic examinations indicative of enlarged lesion.

#### 9.2.2 Secondary endpoints

## 9.2.2.1 Key secondary endpoints

#### 9.2.2.1.1 Efficacy

• ORR based on independent radiology review: objective response rate, confirmed CR + confirmed PR.

## 9.2.2.2 Other secondary endpoints

## 9.2.2.2.1 Efficacy

- Overall survival (OS)
- TBR based on independent radiology review
- PFS based on investigator's assessment
- Disease control rate (DCR, CR+PR+SD) on Week 12 based on independent radiologic review

## 9.2.2.2.2 Safety

- Incidence and severity of treatment emergent adverse event (TEAE), adverse event of special interest (AESI) and serious adverse event (SAE) during the study (including intensive blood collection); severity will be assessed based on NCI-CTCAE V4.03.
- Incidence of adverse events resulting in dose adjustment, suspension and termination of the investigational drug;
- Changes from baseline in ECOG score, vital signs, ECG, left ventricular ejection fraction, dermatological examination and laboratory parameters.

# 9.2.2.2.3 Pharmacokinetics

• After obtaining blood concentration of DCC-2618 and metabolite DP-5439 after single dose and multiple doses, the following PK parameters will be calculated with non-compartment model, including but not limited to  $C_{max}$ ,  $T_{max}$ , AUC and  $T_{1/2}$ , etc.

# 9.2.3 Exploratory endpoint

# 9.2.3.1 Efficacy

• PFS2 based on investigator's assessment: it is defined as the period from the first dose of investigational drug (150 mg, BID) to the first documented tumor progression or death from any cause (whichever is the first) after the dosage is increased to 150 mg (BID).

#### 9.3 Analysis data sets

1) Intent-to-treat (ITT) - Subjects having signed the Informed Consent Form and been included in the trial.

- 2) Full analysis set (FAS): All patients who use at least one dose of the investigational drug.
- 3) Safety set (SS): All patients receiving at least one dose of the investigational drug. In the study, the definition of SS is consistent with FAS. SS is the main population for safety indicator analysis.
- 4) Efficacy analysis set (EAS): all subjects who enter the treatment period and have received at least one dose of the investigational drug, that is, all the patients who have started to receive continuous treatment with the investigational drug since C1D1.
- 5) PK analysis set: all subjects who received at least one dose of the investigational drug and have at least one blood concentration data of DCC-2618 or DP-5439 after administration.
- 6) Per protocol population (PP): subjects in FAS population who do not have expected protocol violations influencing efficacy and/or safety assessment (e.g., the enrolled patient does not comply with critical qualification criteria). Definition of per protocol population will be confirmed before database locking. The PP-based analysis will support the FAS-based analysis.

## 9.4 Statistical methods

#### 9.4.1 General methods

Data collected in the study will be presented using summary tabulations and patients data tabulations. Continuous variables will be summarized with descriptive statistics (number of patients, mean, median, standard deviation, minimum and maximum). Categorical variables will be summarized with frequency and ratio. Time-event data will be summarized with the 25th, 50th (median) and 75th percentile and relevant bilateral 90% confidence interval using Kaplan-Meier (KM).

Unless otherwise specified, baseline measurement values should be the latest values prior to the first dose of the investigational drug. If not assessed, the last assessment before the visit will be used.

Medical Dictionary for Regulatory Activities (MedDRA) will be used to code medical history, adverse event and concurrent diseases. Prior and concomitant medications will be coded according to the Drug Dictionary of World Health Organization (WHODrug).

#### 9.4.2 Subject disposition

All subjects who enter this study (that is, signing informed consent forms) will be summarized. In addition, number of subjects of each analysis data set and number of subjects deleted from each data analysis set (FAS, safety and PP, if applicable) will be summarized. Number and percentage of subjects who finish the study and number and percentage of subjects who withdraw from the study and reasons for drug withdrawal will be summarized.

## 9.4.3 Demographic and baseline characteristics

Descriptive statistic methods will be used to summarize demographics, baseline features, medical history, and concomitant medications before dosing of the investigational drug and during the study in the FAS population.

## 9.4.4 Degree of exposure

Total subjects who receive treatment with the investigational drug will be summarized with number and percentage. Moreover, continuous descriptive statistics will be used to present number of cycles of treatment subjects receive. These analyses will be performed in efficacy analysis population.

## 9.4.5 Efficacy analysis

# 9.4.5.1 Primary endpoints:

# PFS analysis based on independent radiology review

PFS based on independent radiologic review is defined as the time from the first dose of investigational drug (C1D1) to the first documentation of disease progression based on independent radiologic review or death due to any cause (whichever occurs first). Subjects who have previously received surgery for target lesion or non-target lesion, those who have previously received other anti-tumor treatments, and those whose progression or death date is not recorded for any reasons will be censored on the day of the last assessment.

EAS will be used as the main analysis set, with PP as the supporting analysis set. Sensitivity analysis of progression-free survival will be performed, which will be further described in SAP.

# 9.4.5.2 Key secondary endpoints

Critical secondary endpoint is ORR which is defined as the percentage of patients whose efficacy is confirmed as CR or PR based on independent radiologic review after the first dose of the investigational drug (C1D1). This analysis will be carried out in the EAS population as the main analysis and in the PP population as supportive analysis. Confirmation of CR or PR should be carried out at least 4 weeks after patients are first assessed as CR or PR.

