# **Protocol Synopsis**

· · · · · · · · · · · · · · · · · · ·	ГП
	In this study, progression free survival (PFS) based on independent radiologic review is the primary efficacy indicator and RECIST v1.1-GIST Specific Standard is used for tumor efficacy assessment.
	After being fully informed, signing the informed consent forms and passing the screening, the subjects will receive DCC-2618 (150 mg, QD) continuously until the occurrence of an event for treatment termination as specified in the protocol, 28 days as a treatment cycle, followed by a safety follow-up period until 30 days after the termination of study treatment.
	During the study period, the subjects will be subject to visits as scheduled in the protocol. On the day of the scheduled visit as per the protocol, the subjects should bring the drug to the study site, where they will complete all the pre-dose examinations, and take the drug of the day after being suitable to continue the administration, in the discretion of the investigator. In the first four cycles (inclusive), an radiographic examination will be performed within $\pm 7$ days of each cycle and tumor efficacy will be assessed according to RECIST v1.1-GIST Specific Standard. After that, it should be performed within $\pm 7$ days every two cycles.
	If the subject discontinues treatment for reasons other than progressive disease, death, withdrawal of informed consent and lost to follow-up, the subject should receive radiographic examination for tumor assessment by independent radiologic review (IRR) after treatment withdrawal according to the frequency consistent with that during the study until presence of disease progression meeting "RECIST v1.1-GIST Specific Standard" or until starting of new anti-tumor therapy, whichever is the first.
	Based on independent radiologic review, if a subject has a radiologically confirmed progression disease (PD), the subject can choose:
	• To continue DCC-2618, at an increased dose of 150 mg BID, until the occurrence of an event for treatment termination as specified in the protocol; in the case of the efficacy evaluation for such patient, the lesion diameter before the increase of dosage (but not screening period) should be taken as the baseline value.

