17. Radiographic examination during the Screening Period should cover the chest, the abdomen and the pelvis (within 21 days before the first dose). Only abdomen and pelvis are examined during the study; for patients with pulmonary metastases in the screening period or pulmonary metastases symptoms during the study at the investigator's discretion, chest examination should be performed during the study. It is performed once in each of the first four cycles (including Cycle 4), and then once in every two cycles (e.g., Cycles 6, 8 and 10). Initial evaluation of CR or PR should be conformed 4 weeks later at least. Enhanced scanning is required for the examination. MRI may be applied to subjects allergic to CT enhancer to examine the abdomen and the pelvis, with plain CT scanning for the chest. Ensure consistency in examination means during the study. No ultrasonic examination is allowed. If the subject discontinues treatment for reasons other than progressive disease, death, withdrawal of informed consent and lost to follow-up, the subject should receive radiographic examination for tumor assessment by IRR after treatment withdrawal according to the frequency consistent with that during the study until presence of disease progression meeting "RECIST v1.1-GIST Specific Standard" or until starting of new anti-tumor therapy, whichever is the first.

Abbreviations	Chinese Terminology
AE	Adverse Event
ALT	Alanine aminotransferase
AML	Acute myeloid leukemia
ANC	Neutrophil count
APTT	Activated partial thromboplastin time
ASM	Aggressive systemic mastocytosis
AST	Aspartate aminotransferase
ATC	Chemical drug classification system
AUC	Area under the concentration-time curve
β-hCG	Human Chorionic Gonadotropin
BCRP	Breast cancer resistance protein
BID	Twice daily
BP	BP
CI	Confidence interval
CL/F	Apparent plasma clearance
C max	Maximum concentration
СРК	Creatine kinase
CR	Complete response
CSF1R	Macrophage colony stimulating factor receptor
СТ	Computed tomography
CTCAE	Common Terminology Criteria for Adverse Events
СҮР	Cytochrome P450
DCR	Disease control rate
DLT	Dose-limiting toxicity
ECG	Electrocardiogram
ECOG	Eastern Cooperative Oncology Group
eCRF	Electronic Case Report Form
EMA	European Medicines Agency
ЕОТ	End of Study Treatment
ESMO	European Society for Medical Oncology
FDA	Food and Drug Administration

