## 3.1 Overview of Study Design

This study is a multicenter phase 2, single-arm open-label study of DCC-2618 to assess efficacy, safety, and pharmacokinetics in patients with advanced gastrointestinal stromal tumors who have progressed on prior anticancer therapies.

This study targets at the patients with advanced gastrointestinal stromal tumors who have progressed on prior anticancer therapies. It is planned to enroll about 35 subjects in total.

Prior anticancer therapies must include imatinib, sunitinib, and one or two other drugs, and the number of patients who have previously received treatment with  $\geq$  fourth-line drugs should be 40% or less.

In this study, PFS based on independent radiologic review using RECIST v1.1-GIST Specific Standard is used as the primary efficacy measure for tumor efficacy assessment.

After being fully informed, signing the informed consent forms and passing the screening, the subjects will receive DCC-2618 (150 mg, QD) continuously until the occurrence of an event for treatment termination as specified in the protocol, 28 days as a treatment cycle, followed by a safety follow-up period until 30 days after the termination of study treatment.

During the study period, the subjects will be subject to visits as scheduled in the protocol. On the day of the scheduled visit as per the protocol, the subjects should bring the drug to the study site, where they will complete all the pre-dose examinations, and take the drug of the day after being suitable to continue the administration, in the discretion of the investigator. In the first four cycles (inclusive), an radiographic examination will be performed within  $\pm 7$  days of each cycle and tumor efficacy will be assessed according to RECIST v1.1-GIST Specific Standard. After that, it should be performed within  $\pm 7$  days every two c ycles.

If the subject discontinues treatment for reasons other than progressive disease, death, withdrawal of informed consent and loss to follow-up, the subject should receive radiographic examination for tumor assessment by independent radiologic review (IRR) after treatment withdrawal according to the frequency consistent with that during the study until presence of disease progression meeting "RECIST v1.1-GIST Specific Standard" or until starting of new anti-tumor therapy.

Based on independent radiologic review, if a subject has a radiologically confirmed progression disease (PD), the subject can choose:

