#### 6.10 Efficacy

## 6.10.1 Radiographic examination

All subjects will receive radiographic examination of the chest, abdomen and pelvis. See Table 1 for arrangement of time points.

Radiographic examination during the Screening Period should cover the chest, the abdomen and the pelvis (within 21 days before the first dose). Only abdomen and pelvis are examined during the study; for patients with pulmonary metastases in the screening period or pulmonary metastases symptoms during the study at the investigator's discretion, chest examination should be performed during the study. It is performed once in each of the first four cycles (including Cycle 4), and then once in every two cycles (e.g., Cycles 6, 8 and 10).

Radiographic examination must be performed within 21 days before the first dose of drug. Radiographic examination performed before signing an ICF can be used in the Screening Period as long as it is performed within 21 before the first dose and the examination method and result comply with the protocol. Radiographic examination can be performed within  $\pm 7$ days of the scheduled visit . On the basis of independent radiology review, patients assessed as CR or PR in the first assessment should undergo confirmation at least 4 weeks later. Enhanced scan should be performed. If subjects are allergic to CT enhancer, MRI can be performed for abdominal and pelvic examinations and CT for chest examinations as long as examination methods are consistent during the study. Ultrasound examination cannot be performed.

If the subject discontinues treatment for reasons other than progressive disease, death, withdrawal of informed consent and lost to follow-up, the subject should receive radiographic

examination for tumor assessment by IRR after treatment withdrawal according to the frequency consistent with that during the study until presence of disease progression meeting "RECIST v1.1-GIST Specific Standard" or until starting of new anti-tumor therapy, whichever is the first.

Copies of all radiographic scans should be obtained and, according to the regulations, sent to the independent imaging supplier designated by the sponsor. The independent imaging supplier will assess imaging quality and be responsible for independent radiology review.

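### The 28-day minimum for confirming a response equals the scan interval in the first four cycles, so the ±7-day window can make a compliant next scan too early to confirm; the effect on ORR is small and only downward

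*Combined protocol and SAP*

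**What the plan says.** ORR is the key secondary endpoint and counts confirmed responses only: "objective response rate, confirmed CR + confirmed PR" (Section 9.2.2.1.1).

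The minimum confirmation interval appears in three places:
- Section 9.4.5.2: "Confirmation of CR or PR should be carried out at least 4 weeks after patients are first assessed as CR or PR".
- Section 6.10.1, on the basis of independent review: "patients assessed as CR or PR in the first assessment should undergo confirmation at least 4 weeks later".
- Table 1, note 17: "Initial evaluation of CR or PR should be conformed 4 weeks later at least".

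The scan calendar comes from other statements. Treatment runs with "28 days as a treatment cycle" (Section 3.1). On imaging, Section 6.10.1 says: "It is performed once in each of the first four cycles (including Cycle 4), and then once in every two cycles". The Synopsis gives the window: "an radiographic examination will be performed within $\pm 7$ days of each cycle". Section 6.10.1 repeats a ±7-day window around the scheduled visit.

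No section says that the next scheduled scan must be the confirming one, and none sets a latest date for confirmation. Equally, none moves the next scan once a response has been read, or says how a CR or PR repeated at less than 28 days is scored.

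**The concern.** The minimum confirmation interval equals the nominal scan interval, with no allowance for the window. Two subjects with the same tumour course can then be classified differently because of scan dates that the protocol permits.

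Take scans due on C2D1, C3D1 and C4D1 (days 29, 57 and 85). Subject A has PR on days 29 and 57, which are 28 days apart, and progression on day 85. This is a confirmed responder. Subject B has PR on day 32 (+3) and day 56 (-1), which are 24 days apart, and progression on day 85. Read literally, this is a non-responder.

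The error can only remove responders, so ORR, and the responder group used for time to best response, can only be understated. Few responders are expected in a study meant to show consistency with global results, so the scoring of a 24- or 27-day repeat PR is better settled before responses are read.

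**Working it through.** The plan states no confirmation rate, ORR sample size or ORR power, so there is no planned figure to reproduce.

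**Inputs from the documents.** Minimum confirmation interval 28 days (9.4.5.2, 6.10.1, Table 1 note 17). Cycle 28 days (3.1). Scans 4-weekly in the first four cycles, then 8-weekly, each ±7 days (Synopsis, 3.1, 6.10.1). About 35 subjects (3.2). Confirmed ORR of 9.4% in the ripretinib arm of the global phase 3 study (1.3.1.3.2), used for scale only.

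**Assumptions not in the documents.** The distribution of scan dates within the window, and of response duration (taken as exponential from the first PR scan). Scans are placed at C2D1, C3D1, C4D1, C6D1 and so on.

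**1. Interval between consecutive 4-weekly scans.** With offsets e1 and e2 from -7 to +7 days, gap = 28 + (e2 - e1). It runs from 28 - 14 = 14 to 28 + 14 = 42 days.

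**2. Chance that the next scan is too early.** P(gap < 28) = (1 - P(e1 = e2))/2.
- Independent uniform dates: (1 - 1/15)/2 = 7/15 = 46.7%.
- A fraction p exactly on schedule, the rest spread evenly over the other 14 days: P(e1 = e2) = p² + (1 - p)²/14. This gives 36.6% for p = 0.5, 25.2% for p = 0.7 and 9.5% for p = 0.9.
- If sites book the confirming scan at 28 days or later: 0%.

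**3. Later chances to confirm.**
- First PR at Cycle 2: the second following scan (Cycle 4) is 56 ± 14 = 42 to 70 days later.
- First PR at Cycle 3: the second following scan (Cycle 6) is 84 ± 14 = 70 to 98 days later.
- First PR at Cycle 4: the very next scan (Cycle 6) is 56 ± 14 = 42 to 70 days later.

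All of these satisfy the 28-day rule.

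**4. Share of responders never confirmed.** Let g be the interval from first PR to the next scan, h the interval to the scan after that, and S(t) = 2^(-t/m) for median duration m (30.44 days per month). Among subjects with PR on two consecutive scheduled scans, the share lost is E[1(g < 28){S(g) - S(h)}] / E[S(g)], enumerated over all offsets. One instance: g = 24, h = 56 and m = 6 months (183 days) give 1 - 2^(-32/183) = 11.4% no longer in response at the later scan.

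| Scan dates | First PR at | m = 3 months | m = 6 months | m = 12 months |
|---|---|---|---|---|
| Uniform ±7 days | Cycle 2 | 10.1% | 5.2% | 2.7% |
| Uniform ±7 days | Cycle 3 | 17.4% | 9.5% | 5.0% |
| 50% on schedule | Cycle 2 | 7.8% | 4.0% | 2.1% |
| 50% on schedule | Cycle 3 | 13.5% | 7.4% | 3.9% |
| 90% on schedule | Cycle 2 | 2.0% | 1.0% | 0.5% |
| 90% on schedule | Cycle 3 | 3.5% | 1.9% | 1.0% |
| Any | Cycle 4 or later | 0 | 0 | 0 |

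**5. Scale.** Expected responders: 0.094 × 35 = 3.29. If all first respond at the cycle shown, the loss runs from 3.29 × 0.0053 = 0.02 to 3.29 × 0.174 = 0.57 subjects. Divided by 35, that is an average shift in ORR of about 0.05 to 1.6 percentage points. A single reclassified subject moves ORR by 1/35 = 2.9 points, but the expected number reclassified is below one.

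**Limits of the calculation.** It ignores the data cutoff in Section 9 (6 cycles after the last enrolment, or at least 21 IRR-based PFS events if earlier), which could remove a rescuing scan for late enrollees. If the fourth monthly scan is read as falling at day 112 rather than day 84, one more 4-weekly interval is exposed.

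**The case against.** A reader might infer that almost half of early responders would be dropped. The documents do not support this, for two reasons. First, the near-half figure concerns scan intervals and rests on independent, uniform scan dates, which the documents nowhere state. It falls to about 37% to 10% when 50% to 90% of scans are on schedule. Second, an early next scan does not by itself lose a responder, because the rule has no upper limit and every second following scan is late enough. This part of the objection stands, and the calculation above already credits it.

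It can also be said that sites can meet both rules by booking the confirming scan late enough. That is true: when the first scan is at offset e1, the days from e1 to +7 of the next window comply. The choice narrows from 15 days when e1 = -7 to a single day when e1 = +7, and no section tells sites to book from the actual date of the first scan. Investigators read every scan themselves, so they are not blind to response. Whether IRR reads of CR or PR reach them in time is not stated. Section 6.6 allows unscheduled efficacy assessment when clinically indicated, which does not clearly cover confirmation.

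ORR carries no hypothesis, power or success threshold; Section 9.1 rests success on PFS. For 3 responders of 35 the exact 90% interval is about 2% to 21%, far wider than any shift found here. That stands, and it keeps the point minor.

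Finally, Section 9 refers to a SAP for details, and Section 6.10.1 refers to review rules agreed with the imaging supplier. Early repeat scans may be handled in either.

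**Conclusion.** The mismatch is real but its effect is small. A compliant next scan in the 4-weekly phase can fall at 14 to 27 days and fail to confirm. A responder is lost only when no later scan shows response. That is about 0.5% to 17.4% of subjects with PR on two consecutive scans when first PR is at Cycle 2 or 3, and none from Cycle 4: about 0.02 to 0.6 of roughly 3.3 expected responders. The upper end needs uniform scan dates, a 3-month median response duration and every first PR at Cycle 3. The bias runs one way, towards a lower ORR. It touches neither the primary endpoint nor the definition of success. This is a worthwhile clarification and does not call the design into question.

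**What to change.** **Sections 6.10.1 and Table 1 note 17.** State that after a scan read as CR or PR by the investigator or IRR, the next scheduled scan is done no earlier than 28 days after the actual date of that scan. For example, use 0 to +7 days counted from that 28-day point in place of ±7 days around the visit. Say that this takes precedence over the ordinary window, since after a late first scan it can run past it, and that later scans return to the calendar.

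**Section 9.4.5.2.** Keep the 28-day rule for the main ORR. State that any later scan at 28 days or more showing CR or PR confirms the response. If wanted, report ORR counting in-window repeats under 28 days as a sensitivity analysis only. Accepting such repeats in the main analysis is not advised: a 14-day repeat would then count, which relaxes the stated rule in a single-arm open-label study.

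**Cost.** Wording in three places and no extra scan. There is slightly less scheduling freedom for one scan after a first response, and one extra ORR line if the sensitivity analysis is reported.
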